10.2 Secondary Outcomes

1. Treatment failure (i.e. additional parenteral antibiotics) assessed at day 28
2. Escalation in care defined as, escalation in the level of care (i.e. admission from home, admission to intensive care or a high dependency unit) OR change in antibiotic therapy OR death due to poor response. Assessed at 7 and 28 days.
3. Time to defervescence
4. Time to normal feeding (as reported by parent/guardian)
5. Time to normal activity (as reported by parent/guardian)
6. Length of stay
7. Antibiotic-associated adverse events (including diarrhoea and allergic reaction)
8. Antibiotic adherence (full course taken or no more than two missed doses)
9. Paediatric quality of life (measured using PedsQL acute infant version) within 24 hours of randomisation, day 7 and day 28
10. Family impact (measured using PedsQL Family Impact Module acute version) at day 7
11. Health service use and costs

11 SCREENING, CONSENT and RECRUITMENT

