8 TRIAL INTERVENTIONS

8.1 Study Intervention and Comparator (standard care)

When a febrile infant (under three months of age) attends hospital they should undergo blood and urine testing and may receive broad-spectrum parenteral antibiotics in the EDs or assessment unit pending laboratory results. This initial hospital assessment will be unaffected by the EASY study.

Clinicians will be free to perform investigations and administer parenteral antibiotics (standard care) during that initial assessment without delay.

Administration of initial parenteral antibiotics, if required based on national clinical guidelines and local policy, should not be delayed pending consent discussions.

Screening should occur once initial laboratory results are known and only eligible “low risk” infants will be invited to participate in the trial.

Randomisation must occur within 24 hours of hospital attendance.

Eligible “low risk” participants will be randomised in a 1:1 ratio to one of two treatment groups.

Intervention: Oral antibiotics and continuation of oral treatment at least until urine culture results are known (typically after 36 to 48 hours).

Comparator: Continuation of parenteral antibiotics (standard care) at least until urine culture results are known (typically after 36 to 48 hours).

Section 9 of the protocol, outlines the oral and parenteral antibiotics to be used in the EASY study.

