9.7 Study Drug Termination Criteria

Antibiotic treatment may be ended or switched based on clinical assessment during admission or at dedicated telephone reviews. The study drug may also be terminated once urine culture results are known and if no longer clinically indicated.

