12.1 Participant Assessments

The frequency of assessments and follow up are detailed in the schedule of assessments (Table 6). The schedule defines the timing of assessments (with windows) necessary for data collection. Participants should be followed until the final follow-up assessment at day 28, even if antibiotics have been discontinued.

The decision to discharge a participant home is not mandated by the allocation to the oral antibiotic treatment group. The local clinical team should determine when the participant should be discharged and have agreed that it is an appropriate management strategy.

Table 6: Schedule of Assessments

Day/Timepoint	Screening (Day 0)	Baseline (Day 0)	Within 24* Hours of Randomisation	36 – 48* Hours After Randomisation	Follow Up Day 7# (+/- 1 day)	Follow Up Day 28# (+/- 3 days)
At Hospital/Remote	Hospital	Hospital	Hospital/Remote	Hospital/Remote	Remote	Remote
Point of Care Dipstick Urinalysis	x					
Urine sample sent for microscopy and culture	x					
Eligibility	x					
Consent (Trial)		x				
Admission Details		x				
Demographics		x				
Medical History		x				
Symptoms		x	x	x	x	x
Physical Examination		x				
Full Blood Count (including CRP, Creatinine, Electrolytes)		x				
Medications		x	x	x	x	x
Hospital Resource Use			x	x	x	x
Antibiotic Administration (pre randomisation)		x				
Randomisation		x				
Antibiotic Administration (post randomisation) Including Adherence/Tolerability			x	x	x	x
Urine Culture Results			x	x		
Escalation in the level of care/Readmission			x	x	x	x
Adverse Events/ Serious Adverse Events		x	x	x	x	x
[§] PedsQL Infant (completed by parent/guardian)			x		x	x
[§] PedsQL Family Impact (completed by parent/guardian)					x	
SWAT Questionnaire on Consent (completed by parent/guardian)				x		
Health Resource Use and Activities Questionnaire (administered by site staff via telephone)						x

*Assessments will be face-to-face (hospital) or may be by telephone (remote) for participants who have been discharged. Within 24 hours, the parent/guardian should complete the PedsQL Infant Questionnaire. Within 36-48 hours, site staff should remind the parent/guardian to complete the SWAT Questionnaire.

#Assessments will be by telephone (remote) for both cohorts.

At day 7, site staff should remind the parent/guardian to complete the PedsQL Family Impact Questionnaire.

At day 7 and day 28, site staff should remind the parent/guardian to complete the PedsQL Infant Questionnaire.

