14.2.2 Statistical Methods

Baseline characteristics, follow-up measurements and safety data will be described using appropriate descriptive summary measures depending on the scale of measurement and distribution.

Analyses for the primary outcome will be 1-sided and at a significance level of 0.025 and investigated using generalised linear models (GLM) to estimate the risk difference (RD). The difference in treatment failure rate (95% CI) will be compared to the non-inferiority margin of 2%. Non-inferiority is established by showing that the upper bound of a one-sided 97.5% confidence interval for the difference in treatment failure rate is <2%.

A secondary comparison of the primary outcome between the two groups will be investigated using GLM, adjusting for site, sex, age, antibiotic use and other covariates

All remaining analyses for secondary outcomes will be two-sided and at a significance level of 0.05.

Binary outcomes between the two groups will be investigated using GLM, adjusting for covariates.

Comparison of continuous outcomes between the two groups will be investigated using independent t-tests or ANCOVA if appropriate or nonparametric equivalents.

We will include sensitivity analyses looking at treatment failure (day 28) and escalation in care (day 7 and day 28) for those children with a confirmed UTI*.

Statistical diagnostic methods will be used to check for violations of the assumptions, and transformations will be performed where required.

A detailed statistical analysis plan (SAP) will be written by the trial statistician prior to the final analysis.

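### The escalation-in-care composite does not say which antibiotic changes count, so a parenteral-to-oral step-down in the control arm can score as escalation

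*Protocol*

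**What the plan says.** Protocol section 10.2, repeated in the section 1 summary, opens the composite with "Escalation in care defined as, escalation in the level of care (i.e. admission from home, admission to intensive care or a high dependency unit" and completes it with "OR change in antibiotic therapy OR death due to poor response. Assessed at 7 and 28 days". There are three alternatives: a rise in level of care, a change in antibiotics, or death. The reference to poor response comes once, after the last of them.

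Section 8.1 sets the control regimen as "Continuation of parenteral antibiotics (standard care) at least until urine culture results are known (typically after 36 to 48 hours", and the oral regimen as "Oral antibiotics and continuation of oral treatment at least until urine culture results are known (typically after 36 to 48 hours". What follows the culture result is left open. Section 9.7 adds that "Antibiotic treatment may be ended or switched based on clinical assessment during admission or at dedicated telephone reviews", and that treatment may stop once the culture result is known if it is no longer indicated.

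Section 14.2.2 tests secondary outcomes two-sided at 0.05, and plans a further analysis of "escalation in care (day 7 and day 28) for those children with a confirmed UTI".

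Section 10.1 defines the primary outcome in the control arm more narrowly. Only an added, changed or restarted parenteral antibiotic counts, so a move to oral treatment is not a failure there.

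**The concern.** The definition uses a directional word for level of care and a neutral one for antibiotics. On the plain punctuation, any antibiotic change is an event, including one made because the infant is improving.

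The effect differs by arm. A control infant who continues treatment by mouth after the culture result has changed therapy. An oral-arm infant who continues the same drug has not. An outcome named as escalation would then count some de-escalations, mainly among controls, and the comparison would tilt towards oral treatment. Changes made only on culture sensitivities can occur in either arm. They dilute the outcome and need not bias it.

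Two features of the trial raise the stakes. It is open label with unblinded outcome assessors (section 8.2.4), so sites could classify the same event differently. Section 16.2 also exempts events collected as outcomes, including deterioration and readmission, from adverse event reporting. This composite therefore carries part of the safety comparison, and a spurious advantage for oral treatment could hide real deterioration.

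**Working it through.** **1. The plan's own figure.** The protocol states no expected rate or sample size for this composite. The only calculation is for the primary outcome (section 14.1): failure rate 0.5%, margin 2%, one-sided 0.025, power 90%.

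- n per arm = (1.960 + 1.282)² × 2 × 0.005 × 0.995 / 0.02² = 261.4, rounded up to 262, so 524 in total. This matches.
- 524 / 0.90 = 582.2, rounded up to 583. The plan's 584 is the next even number for 1:1 allocation.

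These figures stand. They are used below only for the 262 analysed per arm.

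**2. Which events count under each reading.**

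| Event | Qualifier on death only | Qualifier on every component |
|---|---|---|
| Control infant moves to oral after culture | counts | does not count |
| Change made only on culture sensitivities, either arm | counts | does not count |
| Change because the infant is not responding | counts | counts |
| Treatment simply stopped after a negative culture | unclear | does not count |

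The first row can arise only in an infant on parenteral treatment. An oral-arm infant reaches it only after receiving parenteral antibiotics, which already makes that infant a primary-outcome failure under section 10.1.

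**3. Illustration under the literal reading.** All rates here are assumed. Let e be the true escalation rate, equal in both arms, and s the proportion with a counted switch, independent of e. The observed rate is p = 1 − (1 − e)(1 − s).

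With e = 0.5%, s = 4% in controls and 0% in the oral arm:

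- Control: 1 − 0.995 × 0.96 = 4.48%. Oral: 0.50%. Difference (oral minus control): −3.98 points.
- Standard error under the null, pooled p = 2.49%: √(2 × 0.0249 × 0.9751 / 262) = 0.01361.
- Standard error under the alternative: √((0.005 × 0.995 + 0.0448 × 0.9552) / 262) = 0.01350.
- z = (0.0398 − 1.96 × 0.01361) / 0.01350 = 0.97, so the chance of a significant result favouring oral is about 83%.

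This is a normal approximation with few events. Summing the binomial probabilities of every table significant by Fisher's exact test gives about 82%, so the figure does not depend on the approximation.

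| True escalation, both arms | Counted switches, control / oral | Observed, control / oral | Difference, oral minus control | Chance of false significance favouring oral |
|---|---|---|---|---|
| 0.5% | 4% / 0% | 4.5% / 0.5% | −4.0 points | 83% |
| 0.5% | 12% / 0% | 12.4% / 0.5% | −11.9 points | about 100% |
| 0.5% | 12% / 4% | 12.4% / 4.5% | −8.0 points | 91% |
| 3% | 4% / 0% | 6.9% / 3.0% | −3.9 points | 54% |
| 0.5% | 4% / 4% | 4.5% / 4.5% | 0 | 2.5% (nominal, one side) |

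The 4% and 12% are loosely anchored in section 4.2: confirmed UTI in 4 of 114 low-risk infants (about 4%) and 67 of 555 febrile infants (12%). Using them as switch rates assumes that every control with a confirmed UTI steps down to oral treatment and that no other control does. The 0.5% is borrowed from the primary outcome; the protocol gives no rate for escalation.

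**4. Admission from home.** This component requires an earlier discharge. Section 14.3 expects oral treatment to facilitate earlier discharge, so oral-arm infants are likely to have more time at risk, which pushes against oral treatment. The net direction of the two effects cannot be determined from the protocol.

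**The case against.** The strongest reply is that the qualifier closes a list headed escalation in care and can be read as governing the whole list. On that reading step-down is never an event and the bias disappears. This is a tenable reading, so the defect is an ambiguity and not a plain error. But the protocol does not choose between the readings, and one of them gives an arm-dependent result.

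Event rules for a secondary outcome can also be left to the statistical analysis plan. That does not dispose of the point, because the protocol already states an event rule and the wording of that rule is the problem.

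Some stronger inferences are tempting, and the document does not support them:

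- **Step-down is routine, so nearly all controls with a confirmed UTI would score.** The protocol permits a switch but never describes it as routine, and treatment may simply end. That figure is at most an upper bound.
- **The intended event rate is 0.5%.** That is the assumed primary-outcome rate.
- **The 71% admitted (81 of 114) shows how many controls could not be admitted from home.** It comes from an observational cohort with mixed management and is not a control-arm rate.
- **Only discharged infants can score on level of care.** Intensive care and high dependency admission are open to inpatients. Section 12.1 says "The decision to discharge a participant home is not mandated by the allocation to the oral antibiotic treatment group", and infants in both arms can go home, so the imbalance is one of time at risk. Section 8.2.4 gives realistic evaluation of hospital admission as a reason for the open-label design, so counting such admissions is a defensible pragmatic choice.
- **The comparison is uninterpretable, or this is the leading secondary outcome.** It is one of eleven unranked secondary outcomes, and the confirmed-UTI analysis is a sensitivity analysis.

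**Conclusion.** The concern holds as an ambiguity with a possible arm-dependent consequence. As punctuated, the composite would count parenteral-to-oral step-down as escalation, mainly in controls, and could show a spurious advantage for oral treatment. The confirmed-UTI analysis is the most exposed, because infants who need to continue treatment after culture are concentrated there.

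The size is unknown because the protocol gives no switch rate. In the unequal-switching scenarios shown, the chance of a false significant result runs from 54% to about 100%. With equal counted switching in the two arms, or with the qualifier on every component, there is no bias in the difference. All these figures ignore the opposing time-at-risk effect of admission from home.

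The rewording should be made before analysis. The primary outcome, its margin and the 524/584 sample size are untouched.

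**What to change.** Reword outcome 2 in both section 1 and section 10.2:

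- Make poor response a condition of every component: level of care, antibiotic change and death.
- State that a parenteral-to-oral step-down, and a change made only on culture results, are not events in either arm.
- Report each component by arm alongside the composite, because infants discharged earlier have longer at risk of admission from home.

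Keep the admission component. A new item for prolonged stay would overlap with length of stay (outcome 6) and add another unblinded judgement.

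The cost is a short rewording in two places and a recorded reason for each antibiotic change. The primary outcome does not already supply that reason: section 10.1 turns on what was given, and in the oral arm it counts parenteral antibiotics whatever the cause. Table 6 lists antibiotic administration but no reason for a change, so the case report form may need a field. Unblinded staff will judge the reason. Reporting the components separately lets readers see how much of the result rests on that judgement.

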11.1 Screening Procedure

Participants will be screened from attendances to paediatric EDs and assessment units at recruiting sites. Eligible participants will then be discussed with their clinical team to confirm agreement with trial enrolment. If a participant is initially deemed to be unwell but then becomes well within 24 hours of hospital attendance, they can be reconsidered for participation in the EASY study.

All screening data must be recorded by the Principal Investigator (PI) or designee onto the EASY study screening database. The PI or designee will be required to submit screening data to the CTU each month. Monthly screening data will be used to monitor trial recruitment and provide feedback to sites. The collection of accurate screening data is also required to meet CONSORT 2010 trial reporting guidelines [30].

The outcome of the screening process and reasons for the non-enrolment of potentially eligible participants will be recorded on the EASY study screening database using the Screened, Eligible, Approached, Randomised (SEAR) framework [31]. A minimal dataset will also be recorded for eligible and non-recruited participants which will include age, ethnicity and sex (with the exception of non-recruited participants in Scotland).

Screening: Enter ALL potentially eligible EASY participants who meet the EASY study inclusion criteria onto the screening log:

1. 29 to 90 days of age (Infants from their 29th day of life to their 90th day of life inclusive. Day of birth is day 1 of life)
2. Suspected urinary tract infection (UTI)
3. History of fever as defined as temperature $\geq 38^{\circ}\text{C}$ measured by any method OR likely fever in last 24 hours including subjective fever reported by caregiver
4. Abnormal urinalysis defined as: (1) abnormal urinary dipstick test (leucocyte esterase $\geq 1+$, or nitrite \geq Trace) OR (2) abnormal urine microscopy (≥ 5 white cells per high-power field in centrifuged urine or ≥ 10 white cells per mm^3 in un-centrifuged urine or bacteriuria with any bacteria per high power field)
5. Well on global clinical assessment using the paediatric assessment triangle assessed by a consultant grade doctor

Eligibility Assessment: a physician will confirm the participant's eligibility or reason for exclusion. A participant may be eligible for enrolment assuming the eligibility criteria are met. If the participant is ineligible, the reason will be recorded on the screening log using the following codes:

1. Born at < 30 weeks gestation
2. Discharged from hospital more than 7 days after birth
3. Required re-admission to hospital after birth for more than 24 hours
4. Known or suspected structural renal abnormality
5. Evidence of sepsis and/or meningitis (appear unwell, shock, hypotension, altered mental state, bulging fontanelle, lumbar puncture suggestive of bacterial meningitis)
6. Received vaccination within 48 hours of attendance
7. Sodium $< 128\text{mmol/l}$ on lab or blood gas sample
8. Potassium $> 6.5\text{mmol/l}$ on lab sample
9. Plasma creatinine $> 50\text{micromol/l}$
10. Inability to tolerate oral medication
11. Urine sample was not sent for culture
12. Received additional antibiotics (with the exception of the parenteral antibiotic administered within 24 hours of hospital attendance)
13. Declined consent for participation

Approach: the participant's parent/guardian will be provided with information about the study and asked for their consent. If not approached, enter the reason for non-approach onto the screening log.

If **Randomised:** the participant's Participant Study Number will be recorded on the screening log. If the parent/guardian declined, enter the reason they declined consent on the screening log.

11.2 Informed Consent Procedure

A member of the clinical team will initially approach the parent/guardian of the participant. If the family is interested, they will be introduced to a researcher and presented with the participant information leaflet, consent form and provided with a verbal explanation of the trial procedures. If the trial site has been randomised to the Study Within a Trial (SWAT) intervention (section 15), the parent/guardian will also be provided with an infographic about the study. The family will then be given the opportunity to discuss issues related to the trial with the researcher.

The Principal Investigator (PI) (or designee) is responsible for ensuring that informed consent for trial participation is given for each participant by their parent/guardian. An appropriately trained doctor or nurse may take consent. The person taking informed consent must be GCP trained, suitably qualified and experienced, and have been delegated this duty on the delegation log. Appropriate signatures and dates must be obtained on the informed consent documentation prior to randomisation, collection of trial data and administration of the IMP. If no consent is given the participant cannot be enrolled into the trial.

11.3 Withdrawal of Consent

The parent/guardian may withdraw consent from the study at any time without detriment. If consent is withdrawn this will be documented in the participant's medical notes and in the CRF.

If the parent/guardian declines on-going participation, anonymised data recorded up to the point of withdrawal, will be included in the study analysis unless the parent/guardian requests otherwise.

11.4 General practitioner (GP) Contact

Sites will be advised to send a letter to the participants GP to advise them of their participation in the EASY study.

12 SCHEDULE of ASSESSMENTS

12.1 Participant Assessments

The frequency of assessments and follow up are detailed in the schedule of assessments (Table 6). The schedule defines the timing of assessments (with windows) necessary for data collection. Participants should be followed until the final follow-up assessment at day 28, even if antibiotics have been discontinued.

The decision to discharge a participant home is not mandated by the allocation to the oral antibiotic treatment group. The local clinical team should determine when the participant should be discharged and have agreed that it is an appropriate management strategy.

Table 6: Schedule of Assessments

Day/Timepoint	Screening (Day 0)	Baseline (Day 0)	Within 24* Hours of Randomisation	36 – 48* Hours After Randomisation	Follow Up Day 7# (+/- 1 day)	Follow Up Day 28# (+/- 3 days)
At Hospital/Remote	Hospital	Hospital	Hospital/Remote	Hospital/Remote	Remote	Remote
Point of Care Dipstick Urinalysis	x					
Urine sample sent for microscopy and culture	x					
Eligibility	x					
Consent (Trial)		x				
Admission Details		x				
Demographics		x				
Medical History		x				
Symptoms		x	x	x	x	x
Physical Examination		x				
Full Blood Count (including CRP, Creatinine, Electrolytes)		x				
Medications		x	x	x	x	x
Hospital Resource Use			x	x	x	x
Antibiotic Administration (pre randomisation)		x				
Randomisation		x				
Antibiotic Administration (post randomisation) Including Adherence/Tolerability			x	x	x	x
Urine Culture Results			x	x		
Escalation in the level of care/Readmission			x	x	x	x
Adverse Events/ Serious Adverse Events		x	x	x	x	x
[§] PedsQL Infant (completed by parent/guardian)			x		x	x
[§] PedsQL Family Impact (completed by parent/guardian)					x	
SWAT Questionnaire on Consent (completed by parent/guardian)				x		
Health Resource Use and Activities Questionnaire (administered by site staff via telephone)						x

*Assessments will be face-to-face (hospital) or may be by telephone (remote) for participants who have been discharged. Within 24 hours, the parent/guardian should complete the PedsQL Infant Questionnaire. Within 36-48 hours, site staff should remind the parent/guardian to complete the SWAT Questionnaire.

#Assessments will be by telephone (remote) for both cohorts.

At day 7, site staff should remind the parent/guardian to complete the PedsQL Family Impact Questionnaire.

At day 7 and day 28, site staff should remind the parent/guardian to complete the PedsQL Infant Questionnaire.

At day 28, site staff should administer the Health Resource Use and Activities Questionnaire via telephone.

